This study aims the common disturbance of consciousness in patients with head injury, combined with the application of median nerve electrical stimulation and auricular pressing needle therapy, to observe and analyze the efficacy difference between control group and the experimental group, with the purpose of accelerating the recovery of patients' consciousness, shortening the awakening time, and improving the effect of coma recovery in patients with injury, and to alleviate the economic pressure of society and families to the maximum extent.

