## **Ethics Batch Number (NTC): LLSL-2022053105**

### **4. Research Methods and Design**

#### **1. Subjects**

Sixty patients with head injury treated in our hospital were selected as subjects, randomly divided into control group and experimental, with 30 cases in each group.

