### **3. Observation indicators**

After 4, 6, and 8 weeks of continuous intervention, the awakening conditions, including GCS, GOS outcome evaluation, CRS-R scores, and family satisfaction, were compared.

3.1 Awakening conditions: The time of patient awakening and the awakening at 4, 6, and 8 weeks after intervention were recorded.

3.2 The GCS scale (Glasgow Coma Scale) includes three dimensions: opening, language, and motor, with a full score of 15 points. The lower the score, the worse the patient's neurological function recovery.

3.3 CRS-R (Coma Recovery Scale-Revised): It adds evaluation content such as arousal response, communication ability, and auditory level compared to the GCS scale. lowest score is 0, and the highest score is 23. The higher the score, the higher the level of consciousness.

3.4 Prognosis evaluation was at 1 month after treatment based on the Glasgow Outcome Scale (GOS). A score of 5 indicates good recovery, 4 indicates moderate disability, 3 indicates disability, 2 indicates a vegetative state, and 1 indicates death.

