#### **4.Statistical treatment**

SPSS27.0 statistical software was used for analysis, and the count data of each group was expressed as percentage or composition ratio. The X test was used for the percentage or composition ratio between groups. The measurement data of each group was expressed as mean ± standard deviation (x̄-s). Comparison within the group before and after treatment and comparison between the two groups were performed by t-test. P<0.05 was considered statistically significant.

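### GCS and CRS-R are scored at weeks 4, 6 and 8, but the plan names only t-tests: no arm-by-week contrast is formally estimated and entry GCS is not used in comparing the arms

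*Combined protocol and SAP*

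**What the plan says.** The lead sentence of Observation indicators sets three comparison times for the scores: "After 4, 6, and 8 weeks of continuous intervention, the awakening conditions, including GCS, GOS outcome evaluation, CRS-R scores, and family satisfaction, were compared". GCS is described "with a full score of 15 points"; for CRS-R the "lowest score is 0, and the highest score is 23". Item 3.1 of the same section separately records the time of awakening and awakening status at the three visits.

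Statistical treatment is one paragraph. Counts go to the chi-square test and measurements are summarised by mean and standard deviation. The tests for measurements are given as "Comparison within the group before and after treatment and comparison between the two groups were performed by t-test", and "P<0.05 was considered statistically significant". No repeated-measures analysis of variance, mixed model, summary measure over visits, arm-by-week term or covariate is named.

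Three other places bear on the point. Subjects gives the size, "with 30 cases in each group". The Research idea section presents the trial as run "with the purpose of accelerating the recovery of" consciousness and shortening the time to awakening. Section 1.3 (Termination and handling of the trial) takes the last available result as final for patients removed because of serious adverse events, complications or worsening. Entry GCS must be known for every patient, because inclusion requires a score of 4 to 8.

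**The concern.** Three scores from one patient are correlated, and a t-test at one visit ignores the other two. Testing each visit alone has two consequences.

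First, it does not test whether the arm difference changes between week 4 and week 8. A significant result at week 4 and a non-significant one at week 8 is not evidence of change; that needs the contrast itself with its confidence interval. The before-after tests within each arm do not supply it, because they do not compare arms. This matters because the stated purpose includes speed of recovery.

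Second, precision is scarce at 30 per arm, and information already collected is left out of the between-arm comparison: the other visits and entry GCS.

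**Working it through.** **Inputs from the documents.** 30 per arm; three post-entry visits (weeks 4, 6, 8); significance level 0.05. The documents give no effect size, standard deviation, correlation or power, so there is no stated figure to reproduce.

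**Assumptions.** Two-sided test; equal variance at each visit; the same correlation r between any two visits, with r = 0.6, 0.8 or 0.9; effects in units of the single-visit SD. Power is from the noncentral t distribution with 30 per arm.

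**Single visit.** An effect of 0.6 SD gives 62.8%.

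**Average of three visits.** Variance relative to one visit = (1 + 2r)/3, and standardised effect = (mean of the three visit effects) / √[(1 + 2r)/3].

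| | r = 0.6 | r = 0.8 | r = 0.9 |
|---|---|---|---|
| Variance factor | 2.2/3 = 0.733 | 2.6/3 = 0.867 | 2.8/3 = 0.933 |
| Constant 0.6 SD (mean 0.6) | 0.6/0.856 = 0.701, power 76.1% | 0.6/0.931 = 0.645, power 69.0% | 0.6/0.966 = 0.621, power 65.7% |
| Fading 0.6, 0.4, 0.2 SD (mean 0.4) | 0.467, power 43% | 0.430, power 37% | 0.414, power 35% |
| 0.6 SD at one visit only (mean 0.2) | 0.234, power 14% | 0.215, power 13% | 0.207, power 12% |

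Averaging therefore helps when the effect is constant, and the help shrinks as the visits become more correlated. When the effect fades or is confined to one visit, the average does worse than the t-test at the visit with the 0.6 SD effect (63%).

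**Week-4 minus week-8 contrast, fading pattern.** The difference between arms in change is 0.6 − 0.2 = 0.4 SD, and the SD of a within-patient difference is √[2(1 − r)]. At r = 0.6 this is 0.4/0.894 = 0.447, power 40%; at r = 0.8, 0.4/0.632 = 0.632, power 67%. At r = 0.9 it would be 0.4/0.447 = 0.894, power 93%. Unless visits are very highly correlated, the test of course is weak at this size.

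**Entry GCS as covariate.** If its correlation with the later score is b, residual variance at any visit is multiplied by 1 − b². For b = 0.3, 0.5 and 0.7 the factor is 0.91, 0.75 and 0.51. A 0.6 SD effect at one visit becomes 0.629, 0.693 and 0.840, with power about 67%, 75% and 89% (ignoring the one degree of freedom spent). This gain does not depend on the pattern over weeks, but b is unknown, and the narrow entry range of 4 to 8 may keep it low.

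**Missed visits.** If 15% missed week 8 (30 × 0.85 = 25.5, so 25 and 26 patients) and were left out, the week-8 t-test for 0.6 SD would have 55.6%. This applies only to absences outside the last-result rule in section 1.3, and only if such patients are in fact left out. The plan has no rule for someone who stays in the trial and misses a visit.

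**The case against.** The strongest reply is that the t-tests are valid. In a randomised comparison each one tests the difference in level at its visit, and the planned means and SDs at weeks 4, 6 and 8 would show by eye whether the arms separate and then meet. Speed of recovery is also measured more directly by the time of awakening in item 3.1. All of this stands. A reader might infer that the recovery course is never compared; the documents do not support that. What is absent is a formal estimate of how the arm difference in the scores changes. Nor does the plan literally prescribe one t-test per visit: that follows from three comparison times with one named method.

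A reader might also infer that the t-tests drop every patient who misses a visit. The plan states no complete-case rule, and section 1.3 keeps stopped patients in the analysis with their last result.

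A third tempting reading is that the repeated visits offer free precision. Averaging gains most when the effect is constant, which is exactly when there is no arm-by-week effect to find. The two arguments for a model rest on different patterns and cannot both be claimed at full strength.

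Finally, the arm-by-week term is not by itself a test of faster recovery. Arms that separate before week 4 and then stay apart would show no interaction.

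**Conclusion.** The point holds as a shortfall in efficiency and in formal comparison of the score course. It is not an error that invalidates the planned tests. For a constant 0.6 SD effect, the three-visit average would raise power from 63% to 76%, 69% or 66% at between-visit correlation 0.6, 0.8 or 0.9. For a fading or single-visit effect the average loses power, so it can only supplement the week-specific differences. Baseline adjustment helps under every pattern, as far as entry GCS predicts later scores. All these sizes rest on assumed effects, equal variances and equal correlations, none of which the documents give. The change is worth making because it keeps every comparison the plan wants, adds the missing contrast and needs no new data.

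**What to change.** In Statistical treatment, replace the t-tests for GCS and CRS-R by one repeated-measures model per scale (SPSS MIXED): arm, week (4, 6, 8), arm-by-week, entry GCS as covariate, unstructured covariance across the three visits. Report:

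- the three week-specific adjusted differences with confidence intervals;
- the arm-by-week contrast, with the emphasis on its estimate and interval;
- the average difference over weeks 4 to 8, as a supplement only.

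Add two statements. One should say how the model relates to the last-result rule in section 1.3, since carrying a value forward and modelling the visits actually observed are different treatments of the same patient. The other should say how GCS and CRS-R are treated after death, which the plan foresees as GOS score 1.

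The cost is a revised paragraph and somewhat more analysis work in the named software. The downsides are that a model-based result is slightly harder to explain than a t-test, and that the arm-by-week test has limited power with 30 per arm.

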## **2.Objective**

To investigate the effect of combined electroacupuncture of median nerve and auricular point on the recovery of disturbance of consciousness in patients with crancerebral injury, in order to improve the effect of coma recovery in patients.

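### No outcome or time point is designated as primary, and one P<0.05 threshold covers roughly 8 to 17 implied between-group comparisons with no testing order, adjustment or success rule

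*Combined protocol and SAP*

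**What the plan says.** **Outcomes and visits.** The lead-in to Observation indicators (section 3) reads: "After 4, 6, and 8 weeks of continuous intervention, the awakening conditions, including GCS, GOS outcome evaluation, CRS-R scores, and family satisfaction, were compared". Section 3.1 adds: "The time of patient awakening and the awakening at 4, 6, and 8 weeks after intervention were recorded". Section 3.4 places the GOS at one month after treatment, whereas the lead-in places it at 4, 6 and 8 weeks. Section 3.5 describes family satisfaction as a five-level item and gives no time point of its own.

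**Analysis.** Statistical treatment (section 4) uses chi-square for percentages and, for measurement data, "Comparison within the group before and after treatment and comparison between the two groups were performed by t-test". It closes with "P<0.05 was considered statistically significant". It does not map tests to outcomes or visits.

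**Aims.** The Objective is "To investigate the effect of combined electroacupuncture of median nerve and auricular point on the recovery of disturbance of consciousness". The Research idea section lists several purposes side by side, including "shortening the awakening time, and improving the effect of coma recovery in patients with injury". None is ranked.

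**Size.** Section 1 (Subjects) gives 60 patients, "with 30 cases in each group", with no sample-size calculation.

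**The concern.** Nothing in the available text says which result decides whether adding the ear treatment works. Several scales are compared at several visits, each against the same threshold, and the stated aims are broad enough for most of them to serve as the headline. A plan that is silent here leaves room to report any one significant comparison as evidence of efficacy. The chance that at least one comparison favours the experimental arm by luck is higher than for a single test. The GOS timing conflict adds to this freedom, because the occasion that counts could be settled after results are seen.

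**Working it through.** **Plan's own figures.** The documents state a total of 60 (30 per group) and a per-test threshold of 0.05. The 60 cannot be reproduced, because no power, effect size, SD, event rate or dropout is given. No number of tests and no family-wise error rate is stated.

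**Step 1: count the between-group comparisons** (sections 3 to 3.5).

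| Outcome | Comparisons | Source of ambiguity |
|---|---|---|
| GCS | 3 | none (4, 6, 8 weeks) |
| CRS-R | 3 | none (4, 6, 8 weeks) |
| Time of awakening | 0 or 1 | lead-in may use awakening conditions only as a heading; 3.1 says recorded |
| Awakening at 4, 6, 8 weeks | 0 or 3 | same |
| GOS | 1, 3 or 4 | lead-in against 3.4 |
| Family satisfaction | 1 or 3 | no time point in 3.5 |

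- Awakening tested separately (natural reading): 3+3+1+3 = 10, plus GOS (1, 3 or 4), plus satisfaction (1 or 3), gives 12, 14, 15, 16 or 17.
- Awakening conditions as a heading only: 3+3 = 6, plus the same additions, gives 8 to 13.

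Within-group before-after tests and any adverse-reaction comparisons are not counted.

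**Step 2: reference points.** Sidedness is not stated, so two-sided 0.05 is assumed. A single test with no true effect favours the experimental arm with probability 0.05/2 = 2.5%. If k tests were independent, the chance of at least one would be 1 − 0.975^k: 18.3% (k=8), 26.2% (12), 29.8% (14), 33.3% (16) and 35.0% (17). These outcomes are clearly correlated, so these values are unrealistic upper figures.

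**Step 3: correlated tests.** The test statistics were simulated as multivariate normal with no true effect (1,000,000 draws for k = 12 to 17), with awakening time grouped with awakening status. The documents give no correlations, so a wide grid was used. Entries are the chance of at least one significant result favouring the experimental arm.

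| Within / between outcomes | k=12 | k=14 | k=16 | k=17 |
|---|---|---|---|---|
| 0.5 / 0.2 | 20.6% | 22.9% | 25.2% | 26.2% |
| 0.7 / 0.3 | 17.5% | 19.2% | 20.9% | 21.6% |
| 0.8 / 0.5 | 13.9% | 15.1% | 16.2% | 16.6% |
| 0.9 / 0.7 | 10.1% | 10.8% | 11.4% | 11.6% |
| 0.95 / 0.9 | 6.3% | 6.6% | 6.9% | 7.0% |

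For k=8 the same grid runs from 5.7% to 15.3%. Against 2.5%, the lowest figure is 5.7/2.5 = 2.3 times as large and the highest is 26.2/2.5 = 10.5 times. The simulation ignores deaths and the rule in section 1.3 that takes the last result as final for stopped cases.

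**Step 4: what one deciding test can show.** Take a continuous score with 30 per arm, all analysed and unadjusted:

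- 95% CI half-width: t(0.975, 58) × √(2/30) = 0.517 SD.
- Difference detectable with 80% power at two-sided 0.05: 0.736 SD by the t-test. The normal approximation (1.960 + 0.842) × √(2/30) gives 0.72 SD.

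**The case against.** **The count is an interpretation.** This stands. The analysis section assigns no tests to visits, and the lead-in can be read with awakening conditions as a label for the four scales. A reader might infer that 14 to 17 tests, or at least 12, are definitely planned. The documents do not establish that, and 8 is an available reading. The absence of a ranked outcome does not depend on the count.

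**Not every comparison bears on efficacy.** Family satisfaction is not a stated aim, and GOS is a prognosis measure. Dropping both from the natural reading leaves 10 tests and about 6–17%, still well above 2.5%. A count of 17 also needs GOS on a fourth occasion. If one month after treatment means a month from its start, that roughly coincides with week 4.

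**The rates are assumed, not measured.** Correct. A reader might infer a false-positive chance near one half, since 1 − 0.95^k is 46–58% for 12 to 17 tests. That requires independence and counts results in either direction. Neither fits a false claim of benefit from correlated scales.

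**It is a small exploratory study.** The text never calls it exploratory, and it sets a significance threshold. If that is the intention, saying so would largely answer the point.

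**A primary may be named elsewhere.** Some material was removed before review and no registry record was available, so the finding is limited to the text supplied. Nor does any section say that one significant result will be claimed as success; the plan simply does not rule it out.

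**Conclusion.** The point holds in a limited form. In the supplied text no outcome or visit is primary, and one threshold applies to an unranked set of about 8 to 17 between-group comparisons, with 12 to 17 the natural reading. With no true effect, the illustrative chance of at least one significant result favouring the experimental arm is about 6–26% (6–15% for 8 tests), against 2.5% for one test. This rests on two-sided testing and on assumed correlations from 0.95/0.9 to 0.5/0.2. It is not an estimate of this trial's actual error rate. Confidence is high on the missing primary and lower on the exact count.

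Two further inferences are not supported. First, baseline adjustment cannot be relied on to bring the detectable difference down to about 0.64 SD. That figure assumes a baseline correlation of 0.5, and entry GCS is restricted to 4–8, so the correlation may be lower: at 0.2–0.3 the figure is 0.736 × √(1−r²) = 0.72–0.70 SD. Second, the 0.74 SD figure applies to a continuous score and says nothing about a time-to-awakening analysis.

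**What to change.** Before data are examined:

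1. Name one primary outcome at one time point as the only test that supports an efficacy claim, at two-sided 0.05. One example is CRS-R total at 8 weeks, adjusted for baseline CRS-R if recorded and otherwise for entry GCS, with a stated analysis rule for deaths.
2. Report every other outcome and visit as an estimate with a confidence interval and no significance claim, or test a short named list by Holm or in fixed order.
3. Reconcile the GOS timing between the section 3 lead-in and section 3.4.
4. If data have already been examined, label all results exploratory.

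**Cost.** No added patients; mostly protocol and SAP wording. Adjusting for baseline CRS-R needs that assessment to exist. The before-after comparison suggests it, but no section schedules it, and using entry GCS avoids the need. If time to awakening were preferred as primary, awakening would need a definition and an observation schedule, which the supplied text lacks, and its precision would have to be worked out separately. The main downside is that fewer results may be called significant.

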#### **5.The characteristics or innovations of this topic**

The research is based on evidence-based medicine and uses the median nerve electrical stimulation therapy which is widely used in clinic to increase cerebral blood flow of patients with craniocerebral injury, directly excite the cerebral cortex and the reticular structure of the brainstem, enhance the electroencephal activity, and improve the neuroelectrophysiological activity. In clinical treatment, median nerve electrical stimulation has the advantages of non-trauma, simple operation, low cost, and effective treatment. At the same time, combined with the treatment mode of ear acupressure under the guidance of traditional Chinese medicine meridian acupoint and acupuncture, it can continuously and effectively stimulate the ear

acupoint, improve the excitement and conductivity of acupoint, and achieve the effect of benign and bidirectional regulation. Moreover, can make up for the lack of median nerve electrical stimulation time to the greatest extent, optimize clinical efficacy, further improve the prognosis of patients, and improve the quality of life. to the literature retrieval, there is no literature reporting the same research as this topic in our province, and this topic has a certain degree of innovation. At the same time, the treatment of traditional Chinese and Western medicine is the feature of this project, which can further promote the application of traditional Chinese medicine in clinic.

## **6.Application Prospect**

Disorders of are one of the most common symptoms of craniocerebral injury, with a broad market application and good application prospects. Median nerve electrical stimulation has obvious advantages in promoting awakening the technology is relatively mature, and this treatment method is non-injurious, painless, and less expensive during treatment, and the curative effect is widely recognized by international evidencebased medicine, and it has been widely used in clinical treatment at home and abroad, and the effect of promoting awakening can be guaranteed; ear acupressure has grasped the of traditional Chinese medicine implantation acupuncture of "static and left", which can do a good job of continuous stimulation, and it is safe,

simple to operate, and be applied in community health service centers with poor conditions, and it is easy to replicate and promote.

## **7.The background material of domestic and foreign research progress related to this project**

Although the history of the application of nerve electrical stimulation (MNS) in coma arousal is not long, because of its significant advantages in arousal, MNS has been widely used internationally to treat coma. Cooper [1] et al. were the first to use the right MN to treat patients with closed head injury and coma and achieved certain results. Through several clinical studies, they found that MNS could increase the level of consciousness in patients with TBI and coma, shorten the time of ICU stay (about 10 days), and to some, it could also restore the language function of patients; PeriCV [2] also studied the effect of MNS in treating patients with TBI and coma. After analyzing data, they found that the awakening rate of the stimulation group could reach 60%, while the control group only had 40%, and the stimulation group had higher on the Functional Independence Measure (FIM) scale and more significant improvement in the quality of life. Their research results show that MNS can be used for the arousal of TBI coma and is safe and effective in treatment.

At present, there are few reports on ear acupressure therapy abroad, and in China, it is mostly based different acupoints, which can

play a very good continuous stimulation effect, thus treating various intractable diseases or pain diseases that often occur. Its application range is wide, and can be used in various departments such as internal medicine, surgery, gynecology, and pediatrics. Domestic literature related to ear acupoint treatment is mainly concentrated in earupoint paste, acupressure and other therapies, mostly using round substances such as Semen Vaccariae and magnetic beads to paste on the ear acupoints Jia Jie and Li Xiu Yun [3] used acupoint acupressure combined with ear acupoint paste to assist in the treatment of cerebral hemorrhage disturbance of consciousness and observed that it was effective and easy to operate. He Qing Ming [4] et al. explored the role of ear acupress in the arousal after total anesthesia for craniotomy, and found that it had an exciting effect on the cerebral cortex, could accelerate the arousal, and had the of low cost, few complications, simple operation, and safety. However, at present, there are few studies on ear acupressure therapy at home and abroad, mostly focusing the treatment of insomnia and cognitive dysfunction, and there is still a large blank in the aspect of ear acupressure arousal. Lin Juan [5] et al. ear acupoint embedding therapy combined with electroencephalography to treat insomnia, and found that its curative effect had obvious advantages, and it was found that its treatment method simple and easy to operate, and suitable for popularization and application. Jiao Nini [6] et al. used ear acupressure

to treat cognitive dysfunction after laposcopic hysterectomy, and found that it could regulate autonomic nervous function disorders, relieve neurasthenia, and improve cognitive function by stimulating the heart acupoint kidney acupoint, Shenmen acupoint, sympathetic, and subcortical acupoint, further proving the feasibility of ear acupressure therapy. Li Jun7] et al. used acupuncture combined with ear acupressure to treat insomnia, taking Shenmen, sympathetic, heart, brain, and endocrine acoints, and achieved good curative effect, and found that ear acupressure was more green in treatment, without obvious side effects, and relieved and improved the insomnia of patients, which was worth clinical promotion and application.

